8.1.1 Presentation of Analysis Results (PK analysis excluded)

Based on the results of the central TBx and LBx tests for MET amplification, the following groups of participants will be defined for each treatment arm (combination arm: tepotinib RP2D + osimertinib 80 mg daily, monotherapy arm: tepotinib 500 mg daily) and results presented accordingly:

- T+: participants in the mFAS with a positive central test based on TBx (FISH);
- L+: participants in the mFAS with a positive central test based on LBx;
- Combined (T+ and/or L+): all participants in the mFAS, i.e. with a positive central test based either on TBx or LBx or both tests;
- Other: participants who cannot be considered as T+ or L+ (e.g., participants whose central TBx and LBx test results are both negative or not determined, or participants enrolled under any protocol version who did not progress on first-line osimertinib as the only prior line of therapy).

According to the type of analysis, results may also be presented considering all the participants treated in the combination arm (Total Tepo+Osi), in the monotherapy arm (Total Tepo) and overall (Total).

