After MET amplification positive participants (by central or local TBx, or by central LBx) have given written informed consent for screening procedures, study eligibility will be assessed within -28 to -1 days prior to Day 1 of study intervention. If, at Screening, the participant meets all the protocol-defined inclusion criteria and none of the exclusion criteria, the participant will be considered eligible and will be enrolled into the study. The screening period will include a baseline tumor RECIST Version 1.1 assessment and the confirmation of measurable tumor disease by two independent radiologists. Participants with MET amplification detected locally by FISH must provide tumor tissue at Screening (or at Prescreening) for central confirmation of the result. Central confirmation is not mandated prior to the start of study treatment. Participants who fail to meet the protocol-specified criteria or who discontinue the study before enrollment will be considered screening failures.

Treatment Period

[figure not shown]
During the treatment period of the INSIGHT 2 study, an initial subset of at least 6 participants will be enrolled in a safety run-in treatment part for their first treatment cycle and the rest of the participants will be enrolled directly in the main treatment part as shown in [Figure 2](#) and [Figure 3](#).

[Figure 3](#).

a. SAFETY RUN-IN

An initial subset of at least 6 participants, who are detected to be MET amplified with any of the methods (central/local TBx or central LBx) described at Prescreening, will be enrolled in a safety run-in to confirm the safety of the combination dose of 500 mg once daily of tepotinib as currently used in the Phase II single agent VISION study together with osimertinib 80 mg once daily ([Figure 2](#)).

Figure 2 Safety Run-In

EGFR: Epidermal Growth Factor Receptor; NSCLC: Non-Small Cell Lung Cancer; TKI: Tyrosine Kinase Inhibitor; MET: Mesenchymal-epithelial Transition Factor; amp: amplification; FISH: fluorescence in situ hybridization; NGS: Next Generation Sequencing; TBx: Tissue Biopsy; LBx: Liquid Biopsy.

a Enrollment will be allowed based on positive local FISH testing; tumor tissue must be provided for central confirmation of result by FISH during Prescreening or Screening but central confirmation is not mandated prior to the start of study treatment; if available and allowed locally: additional tissue material to be provided for central TBx NGS.

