- Eligible participants with MET amplification identified by FISH (TBx) (central or local) and independent of the MET status by LBx, will be randomly assigned in a ratio of 2:1 to either the combination of tepotinib at a dose defined by the SMC and osimertinib at the recommended daily dose of 80 mg or tepotinib alone at the daily dose of 500 mg (as currently used in the Phase II single agent study) in cycles of 21-day duration (two-arm study). Participants will continue to receive study treatment until disease progression (according to RECIST Version 1.1), death, AE leading to discontinuation, study withdrawal, or consent withdrawal. The randomization to the two arms of the study will continue until 12 participants who are MET amplification positive by centrally confirmed FISH (TBx) are enrolled in the monotherapy arm. After this, all participants will be assigned to the combination of tepotinib plus osimertinib. For participants in the randomized part of the study, verification of disease progression by IRC is required. Participants who are randomized to the tepotinib monotherapy will have the opportunity to switch over to the combination of tepotinib plus osimertinib if they experience disease progression according to RECIST Version 1.1 reported by investigator and verified by IRC. Until progression is verified by IRC and the switch over to the combination of tepotinib plus osimertinib takes place, tepotinib monotherapy can be continued, if judged appropriate by the Investigator. However, if disease progression is not verified by IRC, the participant must discontinue study intervention. Participants who permanently discontinue tepotinib monotherapy due to an AE, withdraw consent, or for any reason other than progressive disease, will not be eligible to switch over to the combination of tepotinib plus osimertinib.

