Results of the safety run-in treatment part

During the safety run-in treatment period of the MS200095-0031 study, two SMC meetings took place, the first on 05 May 2020 and the second on the 11 August 2020.

In the first SMC meeting, 3 participants who had completed Cycle 1 of treatment with the combination of tepotinib at the dose of 500 mg once daily together with osimertinib 80 mg once daily, were evaluated. No DLTs were noted and the SMC members unanimously confirmed to

continue the safety run-in treatment part without modification, until at least 3 more participants are enrolled in the study. The Investigators agreed with the decision of the SMC members.

In the second and final SMC meeting, 6 participants who had completed Cycle 1 of treatment with the combination of tepotinib at the dose of 500 mg once daily together with osimertinib 80 mg once daily, were evaluated (3 of those 6 participants had newly completed Cycle 1 of treatment since the first SMC meeting). No DLTs were noted with the data evaluated until 11 August 2020. The SMC members unanimously confirmed to continue enrollment in the expansion part of the study with a RP2D of 500 mg tepotinib and 80 mg osimertinib. The Investigators agreed with the decision of the SMC members and no further patients were included into the safety run-in treatment part of the MS200095-0031 study.

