6.3 Measures to Minimize Bias: Study Intervention Assignment and Blinding

This study is performed two-arm, open-label. Once the participant meets all the inclusion and none of the exclusion criteria, the Investigator or delegate will request the study treatment assignment using the Interactive Voice Response System (IVRS). Eligible participants with MET amplification identified centrally or locally by FISH (TBx) will be randomized at a 2:1 ratio to either combination therapy with tepotinib and osimertinib or tepotinib monotherapy. Participants in the Republic of Korea will not undergo randomization but will be assigned exclusively to the combination of tepotinib plus osimertinib, and therefore will not be treated with tepotinib monotherapy. The randomization is implemented in order to assure an objective assignment to the combination and monotherapy to avoid any influence of participant's characteristics on the decision for treatment. The assignment to the two arms will continue until 12 participants with centrally confirmed (FISH testing) MET amplification are included in the monotherapy arm. Afterwards all enrolled participants will receive the combination treatment.

Approximately 20 participants with MET amplification identified by central blood-based next generation sequencing (LBx) only are expected to be assigned to the combination of tepotinib plus osimertinib.

An IRC is implemented to strengthen objectivity and consistency in the evaluation of the primary endpoint.

In addition, an Independent Data Monitoring Committee (IDMC) of external experts will perform periodic reviews and assess benefit risk of the overall study including all participants. This independent review is considered to also improve the overall quality of the data.

Participant numbers will be assigned in the appropriate format and will reflect study number, site number and participant identification. Participant numbers will not be reassigned to other participants or reused in this study. If a participant is replaced, the replacement will be enrolled

with a unique participant number. If a participant is allowed to be re-screened for the study, a new participant number will have to be assigned.

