6/12 (50.0%)	21.1% - 78.9%

CI: confidence interval; ORR: objective response rate.

Total number of participants

Enrollment will continue until 80 participants are included in the primary analysis set, ie, 80 participants with advanced or metastatic EGFRm+ NSCLC and MET amplification, determined centrally by FISH, are included into the tepotinib and osimertinib combination treatment arm.

It is anticipated that approximately 120 participants will be enrolled overall in the study.

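### The SAP defines no group by randomised status, so monotherapy T+ is shown beside a combination T+ column in which about 56 of 80 (70%) are expected to be non-randomised

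*SAP*

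**What the plan says.** **How participants reach each arm**

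- Protocol 6.3 gives the purpose: "The randomization is implemented in order to assure an objective assignment to the combination and monotherapy". Protocol 4.2 adds that the monotherapy arm exists so that tepotinib's contribution to the combination can be judged, with no formal comparison of the arms.
- Randomisation is 2:1 and, in Protocol 4.1, "will continue until 12 participants who are MET amplification positive by centrally confirmed FISH (TBx) are enrolled in the monotherapy arm". Protocol 6.3 then states: "Afterwards all enrolled participants will receive the combination treatment".
- Protocol 6.3 also states: "Participants in the Republic of Korea will not undergo randomization but will be assigned exclusively to the combination of tepotinib plus osimertinib".
- Protocol 4.1 allows entry on a local FISH result: "Central confirmation is not mandated prior to the start of study treatment".
- Protocol 9.4.1 brings eligible safety run-in participants treated at the recommended dose into the same sets. Protocol 4.3 reports 6 evaluated at the second safety committee meeting, after which "no further patients were included into the safety run-in treatment part".
- Protocol 9.2: "Enrollment will continue until 80 participants are included in the primary analysis set", meaning T+ participants on the combination.

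**How results are shown**

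- SAP 8.1.1: "the following groups of participants will be defined for each treatment arm". They are T+, L+, both combined, and Other. Table 1 in SAP 8.1.2 shows both arms in these columns for the main efficacy outputs. The estimand table in SAP 14 also works by treatment and MET test.
- SAP Table 2 adds baseline subgroups for the combination arm only, including pooled region and Chinese status. SAP 14.1.4 plans an ORR with exact interval for each.
- SAP 8.1 leaves Chinese extension participants out of the mFAS at the primary analysis and includes them for the extension and final analyses. SAP 6.4 plans separate Chinese and non-Chinese analyses.

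**The concern.** Every monotherapy participant came through the 2:1 randomisation. The combination T+ column combines four sources: randomised participants, Korean participants, everyone assigned after randomisation closed, and eligible T+ run-in participants. Only the first has an assignment that is independent of country and calendar time relative to the monotherapy arm. At the extension and final analyses the Chinese extension adds further participants. The interim sequence in SAP 6.2 places completion of monotherapy enrolment at the second review, so these late entrants would add to the non-randomised share. Their number is not given.

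Because no test is planned, the side-by-side display is what a reader will use to judge contribution. As specified, a difference between the two T+ columns could reflect period or country as well as treatment, and no specified output gives a response result for the randomised participants alone.

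**Working it through.** **The plan's own figure.** Protocol 9.2 states a 78% probability that the exact 95% lower limit exceeds 35%, given a true ORR of 50% and n = 80. The smallest qualifying count is 37/80 (lower limit 35.03%; 36/80 gives 33.85%). P(X ≥ 37 | 80, 0.50) = 0.783, so the figure reproduces. It concerns the whole combination T+ set, which this point leaves unchanged.

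**Inputs.** Ratio 2:1 and closure at 12 T+ on monotherapy (Protocol 4.1); 80 T+ on the combination (Protocol 9.2).

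**Expected share**

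- Randomised combination T+ = 12 x 2 = 24.
- Non-randomised = 80 - 24 = 56, and 56/80 = 70%.

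The interim triggers in Protocol 9.4.4 and SAP 6.2 also pair 24 combination T+ with 12 monotherapy T+ at completion of monotherapy enrolment. Those 24 are not restricted to randomised participants. If 1 to 6 of them were run-in or Korean (assumed), the share would be 57/80 to 62/80, or 71% to 78%.

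**Spread.** The documents do not state the allocation method, so each row is an assumption.

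| Assumption | Randomised combination T+ | Non-randomised share of 80 |
|---|---|---|
| Simple 2:1, 90% range | 12 to 39 | 85% to 51% |
| Simple 2:1, 95% range | 10 to 43 | 88% to 46% |
| Blocks of 3, all centrally confirmed | 22 to 24 | 72.5% to 70% |
| Blocks of 6, all centrally confirmed | 20 to 24 | 75% to 70% |
| Monotherapy overshoots to 14 T+ | 14 x 2 = 28 | 52/80 = 65% |
| Monotherapy overshoots to 16 T+ | 16 x 2 = 32 | 48/80 = 60% |

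The simple-allocation rows take the number of combination assignments before the 12th monotherapy assignment as negative binomial (12 events, probability 1/3; mean 24, SD 8.5). Under that model the share exceeds 50% with probability about 0.95. Overshoot is possible because central confirmation may follow the start of treatment.

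**Precision of a randomised-only column, at an observed ORR of 50%**

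- Clopper-Pearson 95% interval for 12/24: 29.1% to 70.9%, width 41.8 points.
- For 40/80: 38.6% to 61.4%, width 22.8 points. Ratio 41.8/22.8 = 1.83.

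**Half-width of the arm difference**, normal approximation, with 2/12 on monotherapy as an example:

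- Full column: 1.96 x √(0.1667 x 0.8333/12 + 0.25/80) = 23.8 points.
- Randomised only: 1.96 x √(0.1667 x 0.8333/12 + 0.25/24) = 29.1 points.

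The 12 monotherapy participants dominate the uncertainty, so restricting the combination column costs about 5 points.

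**The case against.** The strongest reply is that the SAP does what the protocol asks. Protocol 9.1 rules out a formal comparison, the monotherapy objectives are stand-alone estimates, and the 12 are justified only by the width of their own interval. Contribution is a design rationale, not an endpoint, and Protocol 6.3 promises no randomised-only display. This stands, and it limits the weight of the point. It does not remove the gain from using a randomisation the trial has already carried out.

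Existing outputs also expose part of the problem. Baseline tables show region and country by arm, SAP 10.1 gives enrolment by country and site and lists first-dose dates, and combination ORRs by region and Chinese status are planned. SAP 6.4 covers much of the Chinese extension. These help with country, but Korea falls inside the Asia level, and none isolates response among randomised participants. The second interim display is close to concurrent, but it is interim and not restricted by assignment route.

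Other points stand in part. The output tracker named in SAP Appendix 4 was not available, so this concerns the SAP text only. SAP section 4 (Purpose of the Integrated Analysis Plan) allows unplanned analyses if the CSR identifies them, so the display could be produced without an amendment, though with less standing. With about 24 against 12, period or country effects could hardly be separated from chance. The new group would also be defined after by-arm outputs reached the sponsor (SAP 6.2, from the second review). Membership depends on assignment route rather than outcome, which leaves little room for selective definition.

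**Conclusion.** The gap is real and modest. No SAP group or subgroup uses randomised status, and the plan's numbers imply that about 70% of the combination T+ column is non-randomised. That rests on 2:1, 12 and 80. It moves to 46% to 88% under simple allocation, and lower if monotherapy overshoots.

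A reader might go further in four ways that the documents do not support:

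- **That 56 of 80 is an observed count.** It is a planning inference; actual counts by assignment route are not in the documents.
- **That the contribution reading is biased in a known direction.** Neither direction nor size can be derived here.
- **That the primary result is weakened.** The combination ORR is a single-arm estimate, and its 78% probability is unaffected.
- **That the run-in supplies at most 6 participants.** Protocol 4.3 reports 6 evaluated; the total enrolled in the run-in and the number T+ are not given.

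The weakness is confined to the descriptive contribution-of-tepotinib reading. The change is worth making, but the trial's main conclusion does not depend on it.

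**What to change.** In SAP 8.1.1 and Table 1, add a supplementary descriptive group, 'T+ randomised': mFAS T+ participants assigned through the 2:1 randomisation, excluding run-in, Korean and post-closure assignments. Beside monotherapy T+, report its number, baseline characteristics, BOR, ORR with Clopper-Pearson 95% CI, and DOR. Label it as supplementary and as added after by-arm outputs were available to the sponsor. Cite it together with the full combination T+ set in any descriptive statement about contribution. Keep the full set as primary and add no test.

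The cost is SAP wording and a few extra columns. This assumes that assignment route can be recovered from the interactive system in Protocol 6.3; the documents describe no such flag. The group is small, so its ORR interval is about 1.8 times as wide as that of the full column. The disagreement between protocol and SAP on monotherapy PFS is a separate matter and not part of this change.

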8.1.2 Analyses per Analysis Set

The following table summarizes the use of the analysis sets and the groups specified above to present the results of the different analysis in tables and figures.

Table 1. Analysis Sets: presentation of the results in tables and figures

Analysis	Analysis set	Results to be presented by
Baseline Characteristics, Baseline Biomarkers, Protocol Deviations, Previous or Concomitant Medications/Procedures	SAF	Tepotinib RP2Dmg + Osimertinib 80mg: T+, L+, Combined (T+ and/or L+), Other, Total Tepo+Osi Tepotinib 500mg: T+, L+, Combined (T+ and/or L+), Other, Total Tepo Total

Analysis	Analysis set	Results to be presented by
Efficacy (excluding sensitivity analyses, subgroup analyses, overall survival and QoL): primary and secondary endpoints	mFAS	Tepotinib RP2Dmg + Osimertinib 80mg: T+, L+, Combined (T+ and/or L+) Tepotinib 500mg: T+, L+, Combined (T+ and/or L+)
Efficacy (sensitivity analysis: start of subsequent anti-cancer treatment, study treatment discontinuation due to COVID-19, subgroup analyses, overall survival and QoL only): primary and some secondary endpoints	mFAS	Tepotinib RP2Dmg + Osimertinib 80mg: T+, L+, Combined (T+ and/or L+)
Efficacy (sensitivity analysis: all participants in the FAS): primary endpoint and some secondary endpoints	FAS	Tepotinib RP2Dmg + Osimertinib 80mg Tepotinib 500mg
Efficacy (Central Nervous System Tumor Response based on RANO- BM criteria): tertiary/exploratory endpoints	FAS/mFAS	Tepotinib RP2Dmg + Osimertinib 80mg: T+, L+, Combined (T+ and/or L+), Other, Total Tepo+Osi (as applicable according to whether FAS or mFAS is presented)
Safety: primary endpoint for the safety run-in	SRIAS	Tepotinib 500mg + Osimertinib 80mg
Safety: all other safety endpoints; Compliance and Exposure	SAF	Tepotinib RP2Dmg + Osimertinib 80mg: T+, L+, Combined (T+ and/or L+), Other, Total Tepo+Osi Tepotinib 500mg: T+, L+, Combined (T+ and/or L+), Other, Total Tepo
Listings (excluding enrollment)	SAF or FAS	SAF for listings presenting baseline and safety data FAS for efficacy listings

8.2 Subgroup Definition and Parameterization

Subgroup analyses will be performed on primary and key secondary efficacy endpoints as defined in Table 2; due to the low sample size in the monotherapy arm, only results for the combination arm will be presented. All subgroup analyses will be exploratory, no adjustment for multiplicity will be performed. Endpoints for which subgroup analyses will be performed can be found in Section 14. In case of low number of participants within a subgroup level (< 5 participants), levels will be pooled when meaningful.

For the definition of subgroup levels, data as documented in the electronic case report form (eCRF) or provided in the SDTM datasets (e.g. country) will be taken. The category "missing" will not be included in any subgroup analysis.

Table 2. Subgroups

Subgroup	Subgroup level	Definition/ Derivation
Age	 < 65 years ≥ 65 years 	Age calculated at the date the screening informed consent is signed. See Section 11.1 for more details.
Sex	MaleFemale	Collected on the "Demographics" eCRF page.
Race	 Caucasian / White Black or African American Asian Other/More than one race 	Collected on the "Demographics" eCRF page. If race is "Not collected at this site" then it will be handled as "missing" (only for the purpose of the subgroup analysis). In case, for example, the race indicated is both "White" and "Asian", the participant will be included in the "Other/More than one race" category.
Pooled Region	AsiaEuropeNorth America	This is derived considering the country where each site is located. The variable "COUNTRY" will be provided in the SDTM demographic dataset.
Japanese Status	JapaneseNot Japanese	Consider as "Japanese" participants enrolled in Japan with "Ethnicity 2" equal to "Japanese". Set to "Not Japanese" all the other participants for which both country and "Ethnicity 2" are available.
Chinese Status	ChineseNot Chinese	Consider as "Chinese" participants enrolled in China with race equal to Asian, not collected at this site or missing. Set to "Not Chinese" all the other participants.
ECOG PS	• 0 • 1	Refer to "ECOG Performance Status" eCRF page. Only participants with score 0 or 1 at Screening should enter the study.
Baseline brain metastases (IRC)	 Present Absent	This subgroup classifies participants according to whether or not they have target or non-target lesions in the brain. This information comes from IRC assessment at baseline.
Baseline brain metastases (Investigator)	PresentAbsent	This subgroup classifies participants according to whether or not they have target or non-target lesions in the brain as per investigator assessment. This information is collected on the "Tumor Assessment (according to RECIST 1.1) – Target Lesions" and "Tumor Assessment (according to RECIST 1.1) – Non-target Lesions" eCRF pages at baseline.
Histopathological classification	AdenocarcinomaSquamousOther	This information is collected in the "Histology" eCRF page.

Subgroup	Subgroup level	Definition/ Derivation
Clinical stage at study entry	AdvancedMetastatic	This information is collected in the "Disease History" eCRF page. The TNM classification at study entry will be used to derive the subgroup levels. See details in Section 18.2.
Time from metastatic disease diagnosis to first dose	 < 6 months ≥ 6 months 	The date of documented metastatic disease diagnosis collected in the "Disease History" eCRF page will be used.
Duration of prior osimertinib	 < 12 months ≥ 12 months 	Duration of prior osimertinib therapy (months) as first and only prior anti-cancer therapy. See Section 11.5 for more details.
Time from disease progression on prior osimertinib to first dose	 < 2 months ≥ 2 months 	Time from disease progression on prior osimertinib therapy as first and only prior anti-cancer therapy to start of study treatment (months). See Section 11.5 for more details.
Mean Gene Copy Number	• < 10 • ≥ 10 • < 8 • ≥ 8	Mean Gene Copy Number resulting from the analysis of tumor tissue samples performed centrally with the FISH test.
MET/CEP7 ratio	• <2 • ≥ 2 • $2-<4$ • ≥ 4	MET/CEP7 (centromere 7) ratio resulting from the analysis of tumor tissue samples performed centrally with the FISH test.
Smoking Status	Current SmokerFormer SmokerNever Smoker	Smoking status derivation can be found in Section 11.6.

9

General Specifications for Data Analyses

This section describes any general specifications not included in subsequent sections.

Presentation of continuous and qualitative variables:

Continuous variables other than PK will be summarized using descriptive statistics, i.e., the number of participants with non-missing values (n), mean, standard deviation, median, 25th percentile (Q1) and 75th percentile (Q3), minimum, and maximum.

Mean, median, Q1, Q3, minimum, and maximum will have the same precision as collected in SDTM datasets for non-derived data. Standard deviation will be presented with one digit more than the mean. Percentage and percent change from baseline will be reported using one decimal

digit, if not specified otherwise. Derived data such as duration and "time since" variables (see Section 9.5) will be displayed with one decimal digit, unless stated otherwise.

Boxplots will be used as graphical representations of the distribution of continuous data (e.g., laboratory values by visit). The center line in the box will present the median whereas the bottom and top lines will present the Q1 and Q3, respectively. Whiskers will extend 1.5 times the interquartile range (i.e., Q3 - Q1) from the top and bottom of the box. If the data do not extend to the end of the whiskers, then the whiskers will extend to the minimum and maximum values. If there are values that fall above or below the end of the whiskers, they will be considered as outliers and plotted as dots.

Pharmacokinetic concentrations will be summarized using n, arithmetic mean, standard deviation (StDev), coefficient of variation (CV in %), median, minimum, and maximum. Summaries of PK parameters will additionally include the geometric mean (GeoMean), the geometric CV (GeoCV in %), and the 95% confidence interval (CI) for the geometric mean (except for t_{max} and t_{lag} which will be summarized using n, arithmetic mean, median, minimum, and maximum only). All data will be analyzed unrounded, but the following rounding conventions will be applied when reporting descriptive statistics for concentrations and PK parameter data, except for t_{max} and t_{lag} which will use the same level of decimal precision (instead of significant digits) as specified below:

Mean, Min, Median, Max, GeoMean, 95% CI:	3 significant digits
StDev:	4 significant digits
CV%:	1 decimal place

Qualitative variables will be summarized by frequency counts and percentages. Unless otherwise stated, the calculation of proportions will be based on the number of participants of the analysis set of interest. Therefore, counts of missing observations will be included in the denominator and presented as a separate category.

For variables where a participant may have more than one category due to multiple responses per participant, the number of participants included in each category will be summarized as a percentage from all participants. Therefore, the total frequency across categories may not equal the total number of all participants in that analysis group.

Scheduled and unscheduled visits

Data collected at both scheduled and unscheduled visits will be included in the derivation of safety and efficacy endpoints.

Descriptive statistics by nominal visit or time point, e.g., for laboratory measurements, will include only data from scheduled visits. Unscheduled visits will be included in the derivation of baseline or worst on-treatment values.

Significance level:

All statistical tests mentioned in this IAP are to be regarded as exploratory. If confidence intervals are to be calculated, these will be two-sided with a confidence probability of 95%, unless otherwise specified in this IAP.

Pooling of sites:

In order to provide overall estimates of treatment effects, data will be pooled across sites. The "site" factor will not be considered in statistical models or for subgroup analyses due to the high number of participating sites in contrast to the anticipated small number of participants treated at each site.

Statistical software:

All analyses will be performed using SAS® Software version 9.2 or higher.

